In addition, a safety follow-up phone call will be conducted at 72 ± 24 hours after DEFINITY® administration.

All echocardiography images will be interpreted by 3 experienced independent blinded readers at a central imaging core laboratory. A single, independent, blinded echocardiologist will read each subject's unenhanced echocardiogram as either optimal or suboptimal. This will be independent of the site investigator determination. All CMR images will be read centrally by a single reader. Echocardiographic imaging data will be compiled, analyzed, and stored without knowledge of the CMR findings.

Study Population:

Approximately one hundred and fifty (150) evaluable subjects will be enrolled at approximately 10 US centers. Subjects who have had a 2D echo with or without contrast or other methods (e.g. CMR, MUGA scan) to evaluate screening LVEF within 6 months prior to enrollment (Day 0) may be enrolled. The study population will consist of males and non-pregnant and non-lactating females 18 years-of-age or older.

Duration of Treatment:

Subjects will receive DEFINITY® treatment once as a part of a single day imaging session.

Study Treatment:

DEFINITY® will be administered as a diluted bolus injection. 1.3 mL of activated DEFINITY® will be diluted with 8.7 mL of preservative-free saline to evenly distribute microspheres. An initial injection of up to 3 mL of diluted DEFINITY® will be administered with subsequent injections of 1 to 2 mL, as needed.

Efficacy Assessments:

The primary endpoint is to demonstrate an improvement in LVEF accuracy from unenhanced imaging to imaging with DEFINITY® contrast enhancement using CMR as the truth standard.

The secondary endpoints are to:

1. Demonstrate improvement in accuracy in left ventricular ejection fraction (LVEF) assessment using DEFINITY® contrast-enhanced over unenhanced echocardiography in subjects with suboptimal echocardiograms.
2. Demonstrate a reduction in inter-reader variability for the assessment of LVEF using DEFINITY® contrast-enhanced versus unenhanced echocardiography.
3. Demonstrate a reduction in inter-reader variability for the assessment of end-diastolic/systolic volumes using DEFINITY® contrast-enhanced versus unenhanced echocardiography.
4. Demonstrate a reduction in inter-reader variability for the assessment of LVEF using DEFINITY® contrast-enhanced versus unenhanced echocardiography in subjects with suboptimal echocardiograms.

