4 STUDY POPULATION

Approximately one hundred and fifty (150) evaluable subjects who have previously undergone a 2D echocardiogram with or without contrast or other assessment (CMR, MUGA scan) will be enrolled in this trial. The study population will consist of male and female subjects 18 years of age or older.

Enrollment will be stratified according to CMR LVEF to achieve an approximately even distribution across four subgroups (LVEF >50, 41-50, 30-40, <30%). LVEF for screening purposes will be determined by the investigator and based on measurements with 2D echo or other methods (e.g. CMR, MUGA scan) obtained within 6 months prior to enrollment (Day 0). Subjects with optimal and sub-optimal echocardiograms will be enrolled. Suboptimal echocardiograms will be based on the site investigator's evaluation of the unenhanced echocardiography images obtained on Day 0. An echocardiogram is considered suboptimal if 2 or more segments of the ventricular border are classified as not adequately visualized in any one of the 3 apical views.

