8.3 Secondary Endpoint(s)

8.3.1 Secondary Efficacy Endpoint(s)

- 8.3.1.1 Improvement in accuracy in left ventricular ejection fraction (LVEF) assessment using DEFINITY® contrast-enhanced over unenhanced echocardiography in subjects with suboptimal echocardiograms

The above primary analyses will be repeated here, but on the subgroup of subjects with suboptimal echocardiograms. There will be no imputation of missing data for this analysis.

- 8.3.1.2 Reduction in inter-reader variability for the assessment of LVEF using DEFINITY® contrast-enhanced versus unenhanced echocardiography

The inter-observer variability among each pair of readers within each imaging modality will be estimated using an intra-class correlation coefficient (ICC). The ICC assesses rating reliability by comparing the variability of different ratings of the same subject with the total variation across all ratings and all subjects. The inter-observer variability in the assessment of LVEF between two readers will be determined by percentage of error. The percentage of error will be calculated using the formula:

Percentage of error = SD between 2 measurements/ mean of the 2 measurements x 100

The mean percentage of error and its 95% confidence interval will be calculated for each pair of readers within each imaging modality.

There will be no imputation of missing data for this analysis.

8.3.1.3 Reduction in inter-reader variability for the assessment of end-diastolic/systolic volumes using DEFINITY® contrast-enhanced versus unenhanced echocardiography

The above analyses used to assess inter-reader variability on LVEF will be carried out, but on end-diastolic/systolic volumes. There will be no imputation of missing data for this analysis.

8.3.1.4 Reduction in inter-reader variability for the assessment of LVEF using DEFINITY® contrast-enhanced versus unenhanced echocardiography in subjects with suboptimal echocardiograms

The above analyses used to assess inter-reader variability on LVEF will be carried out, but on the subgroup of subjects with suboptimal echocardiograms. There will be no imputation of missing data for this analysis.

8.3.1.5 Reduction in inter-reader variability for the assessment of End-Diastolic/Systolic volumes using DEFINITY® contrast-enhanced versus unenhanced echocardiography in subjects with suboptimal echocardiograms

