The above analyses used to assess inter-reader variability on LVEF in subjects with suboptimal echocardiograms will be carried out, but on end-diastolic/systolic volumes. There will be no imputation of missing data for this analysis.

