3.3. Brief Description

This is a Phase 3, prospective, open-label, multicenter study to evaluate LVEF measurement accuracy and reproducibility of DEFINITY® contrast-enhanced and unenhanced echocardiography as compared with non-contrast cardiac magnetic resonance imaging (CMR) used as the truth standard. Approximately one-hundred fifty (150) subjects will be enrolled over approximately 10 months at approximately 10 centers located in the United States. The study population will consist of male and female subjects 18 years of age of older.

Subjects will be screened based on LVEF measurements obtained via 2D echo with or without contrast or other methods (e.g. CMR, MUGA scan) obtained within 6 months of enrollment (Day 0). Subjects will be stratified to achieve an approximately even distribution within four pre-defined LVEF groups (>50, 41-50, 30-40, <30%). LVEF for screening purposes will be determined by the investigator and based on measurements with 2D echo or other methods (e.g. CMR, MUGA scan) obtained within 6 months prior to enrollment (Day 0). The site investigator will determine whether an echocardiogram is optimal or sub-optimal based on the unenhanced echocardiogram performed on Day 0. Subjects with optimal and sub-optimal echocardiograms (based on investigator opinion) will be enrolled. An echocardiogram is considered sub-optimal if 2 or more segments of the ventricular border are classified as not adequately visualized.

Each subject will undergo an unenhanced ultrasound examination and a DEFINITY® contrast-enhanced examination on the same day at Day 0. A minimum of 360 seconds of images will be collected during both the unenhanced and the DEFINITY® contrast-enhanced examinations. Subjects will remain at the clinical site for at least 30 minutes of observation after DEFINITY® administration. A safety follow-up

This document is confidential.

phone call will be conducted for all subjects at approximately 72 ± 24 hours after completion of the imaging sessions, including DEFINITY® administration.

Enrolled subjects will be followed for adverse events (AEs), serious adverse events (SAEs), and changes in concomitant medications from the time the Informed Consent is signed through the safety follow-up telephone call.

A non-contrast CMR will be used as the truth standard. CMR studies will be performed within ±30 days of the echocardiographic assessments at Day 0. Final assignment of each subject to an LVEF group will be determined by CMR.

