Unenhanced and DEFINITY®-enhanced echocardiograms will be performed with standard apical 2 chamber, apical 3 chamber, and apical 4 chamber (A2C, A3C, and A4C, respectively) views using harmonic imaging. Images will be recorded in standard digital format, masked to subject identifiers, and sent to a central imaging core laboratory for analysis.

[figure not shown]
At the central imaging core laboratory, 3 experienced independent blinded readers will interpret the results according to the Image Review Charter. A single, independent, blinded echocardiologist will read each subject's unenhanced echocardiogram as either optimal or suboptimal. This will be independent of the site investigator determination. All CMR images will be read centrally by 1 experienced independent blinded reader.

Echocardiographic imaging data will be compiled, analyzed, and stored without knowledge of the CMR findings.

All screening assessments will occur within 7 days prior to enrollment/DEFINITY® administration (Day 0). CMR studies will occur within ±30 days of DEFINITY® administration. Safety monitoring will continue up to 72 ± 24 hours post-DEFINITY® administration. The expected duration of subject participation is not more than 41 days (see Figure 1).

This document is confidential.

Figure 1. Schedule of Events

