8.2. Secondary Efficacy Endpoint(s) and Analyses

8.2.1. Improvement in accuracy in LVEF assessment using DEFINITY® contrast-enhanced over unenhanced echocardiography in subjects with suboptimal echocardiograms

The primary endpoint analysis will be repeated in the subset of subjects with suboptimal echocardiograms. This will include all primary analyses described in sections 8.1 and 8.1.1, excluding the supportive analyses at the end of section 8.1. The study is not powered to reject the primary endpoint null hypothesis, so the focus is more on the estimate of $\mu_D - \mu_U$, on Bland-Altman plots and on the Deming regression for each blinded reader. There will be no imputation of missing LVEF data for this analysis.

8.2.2. Reduction in inter-reader variability for the assessment of LVEF using DEFINITY® contrast-enhanced versus unenhanced echocardiography

The inter-reader variability among each pair of readers within each imaging modality will be estimated using an intra-class correlation (ICC) and its two-sided 95% CI. The ICC assesses rating reliability by comparing the variability of different ratings of the same subject with the total variation across all ratings and all subjects. The inter-observer variability in the assessment of LVEF between two readers will be determined by percentage of error. The percentage of error will be calculated using the following formula:

$$\text{Percentage of error} = (\text{SD between 2 measurements} / \text{mean of the 2 measurements}) \times 100$$

The mean percentage of error and its 95% CI will be calculated for each pair of readers within each imaging modality. The pairwise ICCs and percentages of error differences will be compared descriptively between contrast-enhanced and unenhanced echocardiography.

In addition, specific to only section 8.2.2, there will also be a separate ICC analysis to assess intra-reader variability as approximately 10% of all echo results will be re-read by each reader.

This document is confidential.

8.2.3. Reduction in inter-reader variability for the assessment of end-diastolic/systolic volumes using DEFINITY® contrast-enhanced versus unenhanced echocardiography

The same analysis used to assess inter-reader variability on LVEF (section 8.2.2) will be conducted for end-diastolic/systolic volumes.

8.2.4. Reduction in inter-reader variability for the assessment of LVEF using DEFINITY® contrast-enhanced versus unenhanced echocardiography in subjects with suboptimal echocardiograms

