
The same analysis used to assess inter-reader variability on LVEF (section 8.2.2) will be conducted for the subgroup of subjects with suboptimal echocardiograms.

8.2.5. Reduction in inter-reader variability for the assessment of end-diastolic/systolic volumes using DEFINITY® contrast-enhanced versus unenhanced echocardiography in subjects with suboptimal echocardiograms

The same analysis used to assess inter-reader variability on LVEF (section 8.2.4) for the subgroup of subjects with suboptimal echocardiograms will be conducted for end-diastolic/systolic volumes.

This document is confidential.

9. Safety

The population used for safety analyses will be the Safety population (SP). Safety will be assessed on the basis of adverse event (AE) or serious adverse event (SAE) reports, physical examinations, and vital signs.

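### Is it left open which reading of the unenhanced echo, site or blinded central, defines the suboptimal subset in three secondary analyses?

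*SAP*

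**What the plan says.** Three of the five secondary endpoints are confined to subjects with suboptimal echocardiograms, and the analysis sections use the term without a source:

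- SAP 8.2.1, LVEF accuracy: "The primary endpoint analysis will be repeated in the subset of subjects with suboptimal echocardiograms".
- SAP 8.2.4, inter-reader variability of LVEF: the analysis "will be conducted for the subgroup of subjects with suboptimal echocardiograms". SAP 8.2.5 carries the same subgroup over to the volumes.
- Protocol 8.3.1.1: "The above primary analyses will be repeated here, but on the subgroup of subjects with suboptimal echocardiograms". Protocol 8.3.1.4 and 8.3.1.5 follow suit, the latter with "The above analyses used to assess inter-reader variability on LVEF in subjects with suboptimal echocardiograms will be carried out".

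The definition stands elsewhere. Protocol 4 says "Suboptimal echocardiograms will be based on the site" investigator's assessment of the Day 0 unenhanced images. The criterion is at least two ventricular border segments poorly seen in any single one of the three apical views. SAP 3.4 repeats both the source and the criterion, Protocol 3.1 assigns the call to the same person, and SAP 3.3 agrees: "Subjects with optimal and sub-optimal echocardiograms (based on investigator opinion) will be enrolled".

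A second classification is also collected. The protocol synopsis says "A single, independent, blinded echocardiologist will read each" subject's unenhanced study, and SAP 3.3 describes that read as labelling the "unenhanced echocardiogram as either optimal or suboptimal. This will be independent of the site investigator determination". Neither document gives this central label a role in any analysis, or says what happens when it disagrees with the site.

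**The concern.** Two labels exist for the same echo, and six analysis sections (three in the SAP, three in the protocol) name neither. The definition in SAP 3.4 sits under subject selection, so it could be read as describing who is enrolled and not who is analysed. A blinded label collected on every subject with no stated use invites the question of what it is for. Two analysts might build different subsets and each point to some text.

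The site call is also open-label. Protocol 5.5 requires no blinding of investigators, and nothing requires the call to be recorded before the enhanced images are seen. Protocol 6.8.1 even says that no analysis is done at the site. If an investigator were more ready to call the baseline study suboptimal after seeing contrast help, the subset would be tilted. Because SAP 8.2.1 says the subset test is unpowered and puts the weight on the estimate, the Bland-Altman plots and the Deming regression, the result would depend heavily on who is in the subset.

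**Working it through.** **1. The plan's own figure.** The only sample-size figure nearby is that for the primary test (SAP 3.5): difference 2.75, SD 10, two-sided 0.05, 150 enrolled, about 5% withdrawal. With 143 evaluable (SAP 10), the noncentrality is 2.75/10 × √143 = 3.29, and the exact paired t-test power is 90.4%, against 90% stated. It reproduces. No size or power is stated for the suboptimal subset, so there is no subset figure to check.

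**2. Is the label defined?**

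| Place | Source of the label | Criterion given? |
|---|---|---|
| Protocol 3.1, Protocol 4, SAP 3.4 | Site investigator, Day 0 unenhanced echo | Yes |
| SAP 3.3 (site call) | Site investigator | Yes, without the clause on the three apical views |
| Protocol synopsis, Protocol 3.2, SAP 3.3 (central read) | Blinded central echocardiologist | No |
| SAP 8.2.1, 8.2.4, 8.2.5; Protocol 8.3.1.1, 8.3.1.4, 8.3.1.5 | Not named | No |

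Wherever suboptimal status is defined with a criterion, the site makes the call. The central read appears only as an additional read, with no criterion in either document. Protocol 3.2 refers to the Image Review Charter for the independent readers' method. The clause missing from SAP 3.3 is a clerical slip, since SAP 3.4 and the protocol carry it in full.

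**3. Can the site call distort the comparison?** There is one treatment group (Protocol 5.4), and each subject has both examinations. The unenhanced views are acquired before drug is given (Protocol 6.8.1), and the call is to rest on them. LVEF is measured by blinded core-laboratory readers (Protocol 6.8.2). The sentence in Protocol 6.8.1 excluding site analysis stands beside the instructions for image transfer. Since Protocol 3.1 and 4 require the site to make the optimal/suboptimal call, that sentence is best read as meaning measurement. The one open route is a call recorded after the enhanced images were seen. The documents show no sign of this, and its effect cannot be derived from them.

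**4. How much rests on the label?** Counts from the text, for the mITT and PP populations:

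- SAP 8.2.1: 3 readers × 2 populations = 6 paired comparisons, plus the bias, RMSE, Bland-Altman, Deming and ICC analyses brought in from SAP 8.1.1.
- SAP 8.2.4: 3 reader pairs × 2 modalities × 2 populations = 12 ICCs and 12 mean percentages of error.
- SAP 8.2.5: the same × 2 volumes = 24 and 24. Total 36 and 36.

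These counts show scope, not bias.

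**5. Would the two labels give different subsets?** This is illustration only, because the documents state neither input. Assume both labels have the same suboptimal share p, with agreement kappa k. Then subjects labelled differently = 143 × 2p(1 − p)(1 − k), and the fraction of the site-defined subset that the central reader would call optimal = (1 − p)(1 − k).

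| p | Subset size | Power per reader at 2.75, SD 10 | Labelled differently, k = 0.8 to 0.4 | Fraction of site subset called optimal centrally |
|---|---|---|---|---|
| 30% | 43 | 42% | 12 to 36 | 14% to 42% |
| 50% | 72 | 63% | 14 to 43 | 10% to 30% |
| 70% | 100 | 78% | 12 to 36 | 6% to 18% |

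For example, p = 0.5 and k = 0.4 gives 143 × 2 × 0.25 × 0.6 = 42.9. Membership could change materially with the label, but step 2 shows that the plan has already chosen one.

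**The case for a change.** The best case for acting is that the remedy is cheap and the label is consequential. One sentence in each of three SAP sections would settle it. A sensitivity analysis on the central label, with a site-by-central agreement table, would need no new reads, and a blinded label is normally preferable to an open-label one. SAP 3.6 keeps the study statistical team blind to reader and CMR results until database lock, so the sentence could be added before results are known to them.

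Part of this stands. The cross-reference is missing, the central read's purpose is unexplained in these two documents, and a tidy SAP would cite SAP 3.4 in 8.2. The rest does not amount to a correction. Making the central read the defining label would replace a definition stated in both documents, with its criterion, by one whose criterion neither gives. It would do so in a SAP that, by its section 2, was to be written following enrollment. It would also be a departure to declare in SAP 11.1. That is a trade-off the sponsor may weigh. The milder course, a cross-reference plus an extra sensitivity table, changes no planned estimate and corrects no wrong result.

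**Conclusion.** No change follows: this is a gap that analysts fill sensibly. A term defined in Protocol 4 and SAP 3.4 keeps that meaning in SAP 8.2, and using the central label for the main subset would be a visible departure from the protocol. The primary success criterion does not involve the subset. The subset accuracy analysis is declared unpowered, and the inter-reader comparisons are descriptive. No bias is shown, and neither its size nor its direction can be derived.

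The conclusion rests on two assumptions. One is that the site call is recorded as Protocol 3.1 and 4 require; neither document shows where it is captured. The other is that the Image Review Charter, which was not available, does not assign the subset to the central read. If it does, the Charter and SAP 3.4 would have to be reconciled. The 12 to 43 subjects in the illustration depend wholly on the assumed shares and kappas.

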An additional secondary objective is to demonstrate a reduction in inter-reader variability for the assessment of LVEF and End-Diastolic/Systolic volumes using DEFINITY® contrast-enhanced versus unenhanced echocardiography. The inter-observer variability among each pair of readers within each imaging modality will be estimated using an intra-class correlation coefficient (ICC); descriptive comparisons of the ICC between DEFINITY® and unenhanced echocardiography will be carried out. Similar analyses will be conducted for the final secondary objective of assessing inter-reader variability within subjects with suboptimal echocardiograms.

TABLE OF CONTENTS

SYNOPSIS.....	2
LIST OF ABBREVIATIONS AND DEFINITIONS OF TERMS.....	11
1 INTRODUCTION	14
1.1 Background.....	14
2 STUDY OBJECTIVES.....	15
2.1 Primary Objective	15
2.2 Secondary Objectives.....	15
3 INVESTIGATIONAL PLAN	16
3.1 Overall Study Design and Plan.....	16
3.2 Rationale for Study Design.....	17
3.3 Study Duration	18
4 STUDY POPULATION	19
4.1 Inclusion Criteria	19
4.2 Exclusion Criteria	19
5 STUDY TREATMENT(S)	21
5.1 Description of Treatment(s)	21
5.1.1 Investigational Product	21
5.2 Treatments Administered.....	21
5.2.1 Administering Study Drug.....	21
5.3 Selection and Timing of Dose for Each Patient.....	21
5.4 Method of Assigning Subjects to Treatment Groups.....	21
5.5 Blinding.....	22
5.6 Concomitant Therapy.....	22
5.7 Treatment Compliance.....	22
5.8 Packaging and Labeling.....	22
5.9 Storage and Accountability.....	22
5.10 Investigational Product Retention at Study Site	22
6 STUDY PROCEDURES	23
6.1 Screening.....	23
6.2 Informed Consent.....	23
6.3 Medical History	23
6.4 Physical Examination.....	24
6.5 Vital Signs.....	24

6.6	Pregnancy Test.....	24
6.7	Cardiac Magnetic Resonance Imaging	24
6.7.1	Image Acquisition.....	24
6.7.2	Imaging Core Laboratory.....	25
6.8	Echocardiography Imaging Procedures	25
6.8.1	Image Acquisition.....	25
6.8.2	Imaging Core Laboratory.....	26
6.9	Efficacy Assessments.....	26
6.9.1	Primary Efficacy Assessments.....	26
6.9.2	Secondary Efficacy Assessments.....	26
6.10	Adverse Event Assessments	26
6.10.1	Performing Adverse Event Assessments	26
6.10.2	Timing.....	28
6.10.3	Severity	28
6.10.4	Relationship	29
6.10.5	Clinical Significance	29
6.10.6	Serious Adverse Events	29
6.10.6.1	Definition	29
6.10.6.2	Reporting Serious Adverse Events	30
6.11	Removal of Subjects from the Trial or Investigational Product	31
7	QUALITY CONTROL AND ASSURANCE	32

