2.2 Secondary Objectives

The secondary objectives of the study are to:

1. Demonstrate improvement in accuracy in left ventricular ejection fraction (LVEF) assessment using DEFINITY® contrast-enhanced over unenhanced echocardiography in subjects with suboptimal echocardiograms.
2. Demonstrate a reduction in inter-reader variability for the assessment of LVEF using DEFINITY® contrast-enhanced versus unenhanced echocardiography.
3. Demonstrate a reduction in inter-reader variability for the assessment of end-diastolic/systolic volumes using DEFINITY® contrast-enhanced versus unenhanced echocardiography.
4. Demonstrate a reduction in inter-reader variability for the assessment of LVEF using DEFINITY® contrast-enhanced versus unenhanced echocardiography in subjects with suboptimal echocardiograms.
5. Demonstrate a reduction in inter-reader variability for the assessment of end-diastolic/systolic volumes using DEFINITY® contrast-enhanced versus unenhanced echocardiography in subjects with suboptimal echocardiograms.

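### Secondary objectives 2–5 promise to demonstrate lower inter-reader variability, but neither document plans an interval for the paired enhanced-minus-unenhanced contrast

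*SAP*

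**What the plan says.** Protocol 2.2 words objective 2 as: "Demonstrate a reduction in inter-reader variability for the assessment of LVEF using DEFINITY® contrast-enhanced versus unenhanced echocardiography". Objectives 3–5 use the same verb for end-diastolic and end-systolic volumes and for subjects with suboptimal echocardiograms. SAP 3.2 repeats all four.

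The analysis is set out in three places:

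- **Protocol synopsis, statistical methods for secondary objectives.** It names only the ICC for the comparison: "descriptive comparisons of the ICC between DEFINITY® and unenhanced echocardiography will be carried out".
- **Protocol 8.3.1.2.** It adds percentage of error, which is the SD between two readers' measurements divided by their mean, times 100: "The mean percentage of error and its 95% confidence interval will be calculated for each pair of readers within each imaging modality". Sections 8.3.1.3–8.3.1.5 carry this to volumes and the suboptimal subset.
- **SAP 8.2.2.** It gives the ICC a 95% CI, repeats the within-modality percentage of error, and then states how the modalities are compared: "The pairwise ICCs and percentages of error differences will be compared descriptively between contrast-enhanced and unenhanced echocardiography". Section 8.2.3 reuses this for volumes. Under 8.2.4 the same analysis "will be conducted for the subgroup of subjects with suboptimal echocardiograms", and 8.2.5 extends that to volumes.

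On the design, SAP 3.3 says: "Each subject will undergo an unenhanced ultrasound examination and a DEFINITY® contrast-enhanced examination on the same day at Day 0". It also says that "3 experienced independent blinded readers will interpret the results according to the Image Review Charter". SAP 8.1 confirms that the three readers read both the enhanced and the unenhanced images.

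**The concern.** To demonstrate a reduction is to make a statement about a difference between modalities. The plan attaches uncertainty to each modality separately but not to that difference. The phrase in SAP 8.2.2 about percentage-of-error differences may mean that point differences will be tabulated; even so, no interval goes with them.

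Both measures are paired by subject. The primary endpoint uses that pairing through a paired t-test (SAP 8.1), and objective 1 repeats that analysis in the suboptimal subset. Objectives 2–5 do not use it. A reader of the study report would have to judge a claimed reduction either from point estimates or from two separate CIs. The first carries little evidence and the second is insensitive. What is at stake is the support for the inter-reader claims.

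**Working it through.** **The plan's own figures.** The documents give no effect size, power, margin or success rule for objectives 2–5, so there is nothing on this point to reproduce. As background, the primary sample size does reproduce. A paired t-test with difference 2.75, SD 10 and two-sided 0.05 needs 141 evaluable subjects for 90% power; 141/0.95 rounds up to 149 enrolled, against 150 stated. Power at 143 is 90.4%. That calculation does not cover objectives 2–5.

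**Inputs for the illustration.** From the documents: n = 143 evaluable (Protocol 8.6, SAP 10), three readers and so three pairs, and 95% intervals. Assumed, because the documents give none: equal SD of per-subject percentage of error in both modalities (the unit below), within-subject correlation ρ, and a true reduction of 0.25 SD.

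**Thresholds**, with t(0.975, 142) = 1.9768:

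- Separate 95% CIs fail to overlap when the difference exceeds 2t/√n = 2 × 1.9768/√143 = 0.331 SD.
- A paired 95% CI excludes zero when the difference exceeds t√(2(1−ρ)/n).

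For ρ, simulated LVEF reads (four equal LVEF strata between 18 and 68, three readers, 4,000 trials per setting) gave a correlation of percentage of error of 0.16–0.18. At ρ = 0.17 the standard error is √(2 × 0.83/143) = 0.1077, so the paired threshold is 1.9768 × 0.1077 = 0.213 SD. At ρ = 0 and 0.3 it is 0.234 and 0.196 SD.

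**Chance of a positive result at a true difference of 0.25 SD** (normal approximation):

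| ρ | Paired CI excludes zero | Separate CIs do not overlap |
|---|---|---|
| 0 | 56% | 25% |
| 0.17 | 63–64% | 23% |
| 0.3 | 71% | 21% |

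For ρ = 0.17: (0.25 − 0.213)/0.1077 = 0.34 gives 63%, and (0.25 − 0.331)/0.1077 = −0.75 gives 23%.

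**Point estimates alone.** With no true reduction, simulated LVEF point estimates favour enhanced echo in at least two of three pairs in about half of trials, as symmetry would suggest, and in all three pairs in about 18%.

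**False signals from the paired CIs.** There are 3 pairs × 3 measures (LVEF and the two volumes) × 2 populations = 18 percentage-of-error comparisons. They were simulated with no true reduction, log-scale read error SD 0.06 or 0.10 on the volumes, LVEF derived from them, and 40% suboptimal (all assumed). At least one unadjusted paired CI favours enhanced echo in about 30% of trials (28–30% across runs). For the three all-subject LVEF pairs alone it is about 7%. At least one of the 18 comparisons shows non-overlap in that direction in about 3%.

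**A property of the metric.** Percentage of error has the mean in its denominator. If enhanced LVEF reads shift up by 3 or 5 points with reader error SD 6 in both modalities, the mean percentage of error falls from 13.4 to 12.2 or 11.6. One pair's paired CI then excludes zero in 14% or 31% of trials. The ICC is unaffected.

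**The case against.** The strongest reply is that the descriptive comparison is deliberate. Both documents choose it openly, and secondary endpoints may be descriptive. The only success rule in the plan is the primary two-of-three-reader rule. The verb is loose elsewhere too: objective 1 also says demonstrate, while SAP 8.2.1 says the study is not powered for it and puts the weight on estimation. Most of this stands, and it is why the point concerns wording and a missing estimate. But SAP 8.2.1 gives that caveat and still repeats the paired analysis; 8.2.2–8.2.5 do neither.

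A second reply is that the sensitivity comparison tests a rule the plan does not have. That also stands. Neither document states a non-overlap criterion or a two-of-three-pair rule, so the percentages illustrate an informal reading and are not operating characteristics of the plan.

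A reader might also infer that the SAP departs from the protocol. It does not: both plan a descriptive comparison. Nor can one infer that the paired CIs should simply become the test of a reduction; the roughly 30% figure shows why not.

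Finally, Protocol 3.1 refers to additional analyses in the Image Review Charter, which is not among the documents. The absence of an interval is established for the protocol and SAP only.

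**Conclusion.** The mismatch between objective and analysis holds in both documents. As planned, the results can describe inter-reader variability within each modality but are a weak basis for saying that a reduction was demonstrated. The textual finding depends on no assumption.

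The size does. At 143 subjects, correlation about 0.17 and a true difference of 0.25 SD, the paired interval would detect the reduction in about 63–64% of trials, against about 23% for an informal reading of separate intervals. The SD, correlation and suboptimal fraction are all assumed. A reader might infer that the primary result is weakened; it is not, because the primary endpoint has its own paired test and success rule. This is a cheap improvement that should be made, not a threat to the trial's main conclusion.

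**What to change.** In SAP 8.2.2–8.2.5, for each reader pair:

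1. Add the mean per-subject enhanced-minus-unenhanced difference in percentage of error, with a paired 95% CI.
2. Add the ICC difference with a 95% CI from a bootstrap that resamples subjects and keeps both modalities together. State the ICC form, which 8.2.2 leaves open.
3. Report all pairs, label these CIs as unadjusted estimates, and note that percentage of error also falls if enhanced LVEF reads merely shift upward.
4. Reword the claims for objectives 2–5 to estimate or describe, unless a multiplicity rule is specified before database lock.
5. List the change in SAP section 11.

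Before lock, this should be done by the statistical team that SAP 3.6 keeps blinded to reader results. The documents do not say whether the database is locked, and SAP section 2 says this SAP was commissioned following enrollment. If it is locked, label the added CIs post hoc.

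The cost is SAP text and minor programming, with no new subjects, images or reads. The price in inference is the false-signal rate given above, which is why the CIs should not carry a claim of demonstration without a multiplicity rule.
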